3. INTRODUCTION, HYPOTHESIS AND OBJECTIVES

3.1 Background

Due to improved prevention, diagnosis and treatment modalities, life expectancy worldwide has risen. The number of adults over 65 years of age who are presenting to emergency services is increasing in parallel with the prolongation of the average life expectancy (1). While geriatric presentations to emergency services comprise 40–50% of all emergency service presentations in the U.S., it has been reported that 3–23% of all emergency service presentations from various regions of the country comprise patients of 65 years of age and older (2–4). There are specific management practices for patients who are 65 years and older at emergency services due to the presence of comorbidities and the change of physiological responses to acute diseases in advanced age (1,2).

Several risk-scoring systems have been developed to define the severity class of the patient during their initial evaluation at emergency services and generally named as Early Warning Scores (5–6). Early Warning Scores (EWS) incorporate physiological measurements, which do predict outcome although the addition of other simple clinical parameters might further improve the sensitivity and specificity of these scores (7). On the other hand all these EWS are simple and easy to calculate, making their use appropriate in an emergency setting (7). Of these EWS, the Modified Early Warning Score (MEWS), and the Rapid Emergency Medicine Score (REMS) have been widely used for many years (8) and The Vital PAC Early Warning Score (VIEWS) score was recently developed for the same purpose (9, 10).

Only a few studies in the literature have evaluated risk-scoring systems for the geriatric patient group. Several studies have reported that risk-scoring systems, such as Identification of Seniors at Risk (ISAR) and Triage Risk Screening Tool (TRST), which are specifically developed for geriatric patients over 65 years who present to emergency services, are not sufficiently effective for evaluating

patients in more severe conditions (11,12). Other studies have reported that the ESI triage classification predicts the prognosis correctly in only half of the patients over 65 years of age (7,13). In another study that evaluated the MEWS for the geriatric patient group, which was calculated during the presentation in emergency services, has been stated to have a prognostic value in terms of a poor result (14).

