3.2. Study objectives

MAIN OBJETIVE

The main objective of this project will be

- To determine Epidemiologic and Age Related Characteristics of Geriatric Patients presenting to the ED across Europe.

SECONDARY OBJETIVES

- To evaluate Early Warning Scoring systems (REMS, MEWS and VIEWS Scores) and determine most suitable Geriatric Emergency Medicine Risk Score regarding hospitalization, ICU admission and in-hospital mortality for patients
- To determine the most effective triage elements that can be used to predict hospitalization of geriatric patients presented to ED

- To determine the in hospital mortality and short term mortality rates of the patients above 65 years of age presenting to the ED across Europe.
- Sub analysis of ED discharged patients versus admitted patients for characteristics, comparison to recommended care and re-ED visit.
- Comparison of European data characteristics, investigation, treatment and outcome to similar data in other part of the world.

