5.4. Variables included on the study

Variables are reflected on the Case Report Form

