6. TREATMENT

No modification on the selected management is required.

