11. ANALYSIS

11.1. Data Analysis

Patients will be classified based on their ages, emergency medicine diagnosis and early warning scores.

The normality analyses of the data will be performed using the Kolmogorov-Smirnov and Shapiro-Wilk tests. The data did not comply with normal distribution. The continuous variables will be expressed as the median (inter-quartile range), and the categorical variables were expressed as a number (percentage). The inter-group differences between the continuous variables will be evaluated using the Kruskal-Wallis test and the Mann-Whitney U test (with Bonferroni correction). The inter-group differences between the categorical variables will be evaluated using the Chi-square and Fischer Exact tests. The predictive power of the scores for hospitalization and mortality in hospital will be evaluated using the Receiver Operating Characteristic (ROC) analysis. The values of the Areas Under the ROC Curve (AUC) will be evaluated. The optimum cut-off points of the scores will be determined for both of the main endpoints using the Youden index (sensitivity+specificity-1).

Using these determined cut off points for the sensitivity, specificity, positive predictive value, negative predictive value, likelihood ratio (+) and likelihood ratio (-), the values of both the scores will be calculated for both hospitalization and mortality at the hospital. Graph representation will be used to increase understanding of data.

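### The scores are compared partly on hospitalisation, a usual-care decision that a score already in use may inform, and the visible plan neither records nor analyses such use

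*Combined protocol and SAP*

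**What the plan says.** - **Aim.** A secondary objective in section 3.2 is to evaluate REMS, MEWS and VIEWS and "determine most suitable Geriatric Emergency Medicine Risk Score regarding hospitalization, ICU admission and in-hospital mortality for patients".
- **Method.** Section 11.1 states: "The predictive power of the scores for hospitalization and mortality in hospital will be evaluated using the Receiver Operating Characteristic (ROC) analysis". It adds: "The values of the Areas Under the ROC Curve (AUC) will be evaluated", and "The optimum cut-off points of the scores will be determined for both of the main endpoints using the Youden index". The two main endpoints are hospitalisation and in-hospital mortality. Nothing says which one decides. No ROC analysis of ICU admission is described.
- **Management.** Section 6 leaves care as it is: "No modification on the selected management is required". No section blinds the deciding clinicians to any score.
- **Existing use.** Section 3.1 says MEWS and REMS "have been widely used for many years (8" (the final figure is a reference number), whereas the VIEWS "score was recently developed for the same purpose".
- **Data.** Section 5.4 says: "Variables are reflected on the Case Report Form". The form in Appendix 1 collects vital signs, Glasgow Coma Score and disposition. It has no item on whether a score was calculated, seen or used. The Appendix 2 site questionnaire is only partly visible.

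**The concern.** A prognostic comparison needs an outcome that the predictors did not help to produce. Death in hospital is not itself an ED decision. Admission to a ward or to ICU is. Where staff consult a score when deciding on admission, that score becomes part of the outcome it is later credited with predicting (incorporation bias). The effect is differential: the score in use gains more than one not in use.

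At stake is the statement of which score is most suitable regarding hospitalisation. It could partly reflect which score EDs already use. Section 11.1 has no stratification, sensitivity analysis or caveat that would reveal this.

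**Working it through.** **1. Inputs from the documents.** Sections 5.6 and 11.3.1 give 40-50 sites and at least 25 patients per site: 40 × 25 = 1,000 and 50 × 25 = 1,250. Section 3.1 gives pilot in-hospital mortality of about 6%. No AUC, effect size, extent of score use or hospitalisation rate for the ED population is stated, so there is no planned figure to reproduce. Everything below is an assumption used to test the mechanism.

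**2. Three equally good scores.** Severity is N(0,1) and each score correlates 0.6 with it. Logit of admission = constant + 1.0 × severity + log(OR) × [score 1 is high and the ED uses score 1]. With no use, each score ranks first in about one third of studies. With score 1 used in 25% of EDs:

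- If the scores share nothing but severity, their pairwise correlation is 0.6 × 0.6 = 0.36. Score 1 then ranks first in about 44% of studies at OR 2. At OR 4 the figure is 59-83%, depending on how the score is scaled.
- All three scores use overlapping vital signs, so higher correlations are plausible. At OR 4, score 1 ranks first in 70% at correlation 0.7, and in 55-65% at 0.8.
- Much of the spread comes from how common a high value is. I repeated the model with 45 EDs × 25 patients, constant -0.7 and 800 replicates. At OR 4, moving the cut-off from the score's mean to 1 SD above it changed first place from 84% to 61% at correlation 0.36 (AUC gain 0.025 to 0.013), and from 66% to 45% at correlation 0.8 (gain 0.009 to 0.004).

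This gives roughly 45-85% and a gain of about 0.005-0.025. The mildest combination tried (OR 2, high cut-off, correlation 0.8) fell just below, at 41% and 0.002.

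**3. Use split between two scores** (25% of EDs in total, OR 4). The advantage of either used score shrinks: at correlation 0.8, one run gave a gain of about 0.002 and first-place shares of 38%, 35% and 26%. The unused score still loses, ranking first in 15-19% of studies in another run and 26% in this one, against a fair 33%.

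**4. Can a better score lose?** Take two scores correlating 0.50 (A) and 0.55 (B) with severity and 0.6 with each other, 35% hospitalised, N = 1,000. The admission variable is severity + noise, plus 0.5 × A for the share of patients treated where A is used. A outranks the better B with probability 0.17 with no use, 0.47 at 25% use and 0.79 at 50%.

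**5. Mortality.** In the two-score model with equal scores, whole-cohort AUCs for death stay equal within about 0.006, which is simulation noise. Deaths may be few, however. If 6% applies to hospitalised patients and 20-50% are hospitalised (assumed), expect 1,000 × 0.20 × 0.06 = 12 to 1,250 × 0.50 × 0.06 = 37.5. If it applies to everyone, expect 60-75.

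**6. Does the remedy work?** Restricted to non-user EDs, score 1 returned to first place in about one third of studies in every three-score setting tried.

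**The case against.** The strongest reply is that the premise is inferred. No section says a participating ED admits on MEWS or REMS. Section 3.1 presents early warning scores as grading severity at initial evaluation, which is triage rather than disposition. Its pilot summary suggests the scores might be considered in triage, which reads as future use. The reference behind the wide-use statement introduces REMS as a new tool. All this stands, and it is why the size cannot be stated and why use should be recorded.

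Three stronger readings are tempting and not supported:

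- **That hospitalisation decides the choice.** Sections 3.2 and 11.1 also name in-hospital mortality, and no selection rule exists.
- **That the study is meant to settle established against newer scores.** No objective says so, and the pilot credited MEWS and VIEWS, one older and one newer, with higher sensitivity and specificity for mortality.
- **That the choice should therefore rest on mortality alone.** That would drop outcomes named in the objective and might rest on few deaths.

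It is also fair that stratifying by score use does not make admission independent of the vital signs, which clinicians see everywhere. It removes the preferential advantage of the score in use, not that shared influence. Finally, the part of Appendix 2 not shown may already ask about triage tools. Even then, section 11.1 does not use the answer.

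**Conclusion.** The concern holds conditionally. Hospitalisation is one of two main ROC endpoints and is a usual-care decision. The protocol itself describes unequal uptake of the scores, and the visible plan neither records nor analyses use. Wherever a score informs admission, its hospitalisation AUC and Youden index are biased upwards relative to a score not in use. The same would apply to ICU admission if it were analysed.

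The real size is unknown. The simulated range illustrates single-score use in a quarter of EDs at an assumed odds ratio of 2 to 4. It shrinks with strong correlation or split use, and is nil if no ED uses a score for admission. The documents therefore do not show that the ranking will be wrong, only that the plan could not tell. The weight is low to moderate: a secondary objective is affected, the main descriptive aim is not, and the remedy is cheap.

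**What to change.** 1. **Appendix 2:** add one item per site, unless the part not shown already has it: which of MEWS, REMS, VIEWS/NEWS, other or none was used in triage or admission decisions during the study week. Section 10.3.2 accepts no changes during recruitment, so this belongs before it starts.
2. **Section 11.1:** report hospitalisation AUCs (and ICU-admission AUCs if computed) overall and separately for user and non-user EDs.
3. **Section 11.1:** call a score most suitable regarding hospitalisation only if its ranking also holds in non-user EDs. Otherwise, describe the overall AUC as partly reflecting current practice.
4. Keep in-hospital mortality as a separately reported endpoint, not the sole basis for the choice.

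**Cost:** one question per site, one stratified table and a few sentences, with nothing added per patient. Intervals widen in the non-user stratum. If 25% of EDs are users, 750-938 of 1,000-1,250 patients remain, and intervals are about √(1/0.75) = 1.15 times as wide. At 50% use the factor is √2 = 1.41. The shared influence of vital signs on admission remains and should be stated as a limitation.

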Previously the TEDGeS (Turkish Emergency Departments Geriatric Scoring Study) pilot study was carried out and published (15,16). This study enrolled all geriatric patients (age ≥ 65 years) and carried out in 13 centers (University Hospitals, Government Education and Research Hospitals and Military Hospital ED) from different cities of Turkey.

Key findings were:

- Overall 30 % of hospitalized patients from ED are elderly patients and 30 % of these hospitalized patients were ICU hospitalizations
- In hospital mortality rate is about 6 % which is very high for general hospitalized patients
- The most common presenting symptoms are related to gastrointestinal systems and about 80 % of the cases using at least one chronic medication (22.2 % of the cases using more than 4 chronic medications)
- About 45 % of the cases final diagnosis are related to cardiovascular system and gastrointestinal system and nearly 85 % of the hospitalized cases are treated in non-surgical clinics (cardiology-pulmonology-internal medicine 65 %)
- MEWS, VIEWS and REMS scores are significantly high in hospitalized patients compared to discharged from ED and also these three scores are high in ICU hospitalized patients compared to both ward hospitalized and discharged patients.

- MEWS, VIEWS and REMS scores are significantly high in non-survivors compared to survivors.
- MEWS, VIEWS scores has higher sensitivity and specificity in terms of in-hospital mortality

These results suggest that geriatric patients not only constitute significant proportion of ED presentations but also they need more hospitalization. The predictive powers of the MEWS, VIEWS and REMS scores for hospitalization and mortality in geriatric patients those presented to ED are significantly high and might be concerned in the ED triage of these patients.

References

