5.6. Sample size

- ✓ All of the patients over 65 years who had presented to emergency services due to acute medical or surgical reasons during the 7 days study period are to be included. Patients younger than 65 years of age will be excluded from the study. The patients who had been brought to emergency services after having undergone cardio pulmonary resuscitation by the emergency medical team will be also excluded from the study.
- ✓ We strive for at least 25 patients per site per study period with a complete case report form (CRF). (This number is based on our pilot study, TEDGeS - Turkish Emergency Departments Geriatric Scoring Study)
- ✓ Each participating center will have to enroll all consecutive cases.

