11.3.1. Sample size

As this is a descriptive study, a formal sample size calculation has not been performed.

Based on our past experience of similar studies, we would expect to enroll between 40 and 50 sites each with an average number of patients of at least 25/site per 7 days study period.

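### Section 11.1 picks each score's cut-off by the Youden index and reports accuracy there in the same patients, uncorrected and without confidence intervals; mortality sensitivity and likelihood ratios will be too favourable on average

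*Combined protocol and SAP*

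**What the plan says.** Section 11.1 plans ROC analysis of the scores for hospitalization and in-hospital mortality. On the AUC it says only: "The values of the Areas Under the ROC Curve (AUC) will be evaluated". On thresholds: "The optimum cut-off points of the scores will be determined for both of the main endpoints using the Youden index (sensitivity+specificity-1". Accuracy then follows from the chosen thresholds: "Using these determined cut off points for the sensitivity, specificity, positive predictive value, negative predictive value, likelihood ratio (+) and likelihood ratio (-), the values" are to be calculated for both endpoints.

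Neither 11.1 nor any other section mentions a confidence interval, standard error, resampling, hold-out sample or threshold fixed in advance. The Bonferroni correction in 11.1 belongs to the Mann-Whitney comparisons.

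Section 3.2 gives the purpose, a secondary objective: to "determine most suitable Geriatric Emergency Medicine Risk Score regarding hospitalization, ICU admission and in-hospital mortality for patients". Section 11.3.1 has no formal sample size calculation and expects "between 40 and 50 sites each with an average number of patients of at least 25/site". That is a minimum, since Section 5.6 adds: "Each participating center will have to enroll all consecutive cases". The only guide to the number of deaths is the pilot result in Section 3.1: "In hospital mortality rate is about 6 % which is very high for general hospitalized patients".

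**The concern.** There are two separate gaps.

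**Selection.** The cut-off is placed where sensitivity plus specificity happens to be highest in this sample. Part of that peak is chance, and evaluating the cut-off in the same patients counts the chance part as accuracy. The effect depends mainly on the size of the smaller outcome group. For mortality that is the deaths, so it falls on sensitivity and the likelihood ratios far more than on specificity.

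**Unreported uncertainty.** Without intervals a reader cannot see that the mortality figures may rest on a few dozen deaths, or whether two scores differ by more than chance. This does not bias anything, but it matters for an objective that aims to name the most suitable score.

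The selection effect also grows with the number of levels a score has. Three scores compared at their own Youden cut-offs therefore need not be flattered equally.

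**Working it through.** **Plan's own figure.** There is none to reproduce. The only arithmetic available is 40 × 25 = 1,000 and 50 × 25 = 1,250 patients (11.3.1). Because this is a minimum, three times N (3,000–3,750) is shown as well.

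**Expected deaths.** The denominator of the pilot's 6% (3.1) is not explicit, so both readings are used.
- All enrolled: 1,000 × 0.06 = 60; 1,250 × 0.06 = 75. At three times N: 180–225.
- Admitted only, with 30–40% admitted (assumption): 1,000 × 0.30 × 0.06 = 18; 1,250 × 0.40 × 0.06 = 30.

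**Sampling error of sensitivity.** Wilson 95% half-width = z/(1 + z²/n) × √[p(1−p)/n + z²/(4n²)], with illustrative p = 0.65, n = deaths and z = 1.96. For n = 60: (1.96/1.0640) × √(0.003792 + 0.000267) = 0.117, or 11.7 points. Likewise 10.6 (75 deaths), 20.2 (18), 16.2 (30), 6.9 (180) and 6.2 (225).

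**Sampling error of one AUC.** Hanley-McNeil: variance = [A(1−A) + (d−1)(Q₁−A²) + (m−1)(Q₂−A²)]/(d·m), with Q₁ = A/(2−A), Q₂ = 2A²/(1+A), d deaths and m survivors. For A = 0.65, d = 60, m = 940: (0.2275 + 59 × 0.0590 + 939 × 0.0896)/56,400 = 0.00156, and 1.96 × √0.00156 = 0.077, or 7.7 points. Over A = 0.65–0.80 the half-width is 6.1–7.7 points at 60–75 deaths and 9.6–13.9 at 18–30.

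**Selection bias.** Simulation: binormal score cut to 7, 9, 11 or 15 levels, two level spacings, true AUC 0.65–0.80 (all assumptions), 8,000 replicates per setting. The cut-off is the sample maximum of sensitivity + specificity − 1. Bias is the apparent value minus the population value at that same cut-off. Figures are in percentage points.

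| Deaths / patients analysed | Sensitivity half-width | Sensitivity bias | Specificity bias | PPV bias |
|---|---|---|---|---|
| 60/1,000 to 75/1,250 | 11–12 | 1.5–4.5 | 0.3 or less | under 1 |
| 180/3,000 to 225/3,750 | 6–7 | 0.5–2 | 0.3 or less | under 1 |
| 18/1,000 to 30/1,250 | 16–20 | 3–10 | 0.3 or less | under 1 |
| 18/300 to 30/500 (admitted only) | 16–20 | 3–10 | 0.2–0.6 | 0.9–2.0 |

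- Likelihood ratios: LR− is too low by about 5–11% and LR+ too high by 2–9% at 60–75 deaths; about 10–24% and 4–19% at 18–30.
- Number of levels, at 60–75 deaths: sensitivity bias is 1.5–2.9 points with 7 levels and 2.2–4.3 with 15.
- Single studies: apparent sensitivity was below the true value in 21–40% of runs at 60–75 deaths and 13–35% at 18–30.
- Hospitalization (30–40% admitted, assumption): sensitivity bias is about 0.2–1.2 points.

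A second simulation, with rounded-normal scores and AUC 0.65–0.85, gave the same direction in every mortality setting. Example at AUC 0.75, apparent against true: with 18 deaths of 300, sensitivity 0.683 against 0.609 and LR+ 3.52 against 2.86; with 60 of 1,000, sensitivity 0.648 against 0.617 and LR+ 2.86 against 2.67.

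**The case against.** The strongest case for the plan is this. The study calls itself descriptive. The three scores are existing instruments, not fitted here. The AUC is planned and does not depend on a cut-off. The bias is small beside the sampling error and shrinks if sites enrol well above 25. Even uncorrected, a Wilson interval at the apparent sensitivity covered the true value in 90.0–96.9% of simulated studies, so asking for intervals alone would meet most of the need.

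Much of this stands, and it rules out three stronger readings that a reader might infer.
- *The mortality figures will be inflated.* Only on average; in a sizeable minority of simulated studies the apparent sensitivity was too low.
- *The choice of score will be biased.* Section 11.1 does not say which measure decides. If the AUC decides, the cut-off selection does not touch the ranking.
- *All the accuracy results are compromised.* Hospitalization has too many events for that, and the missing intervals bias nothing.

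The rest does not stand. Section 11.3.1 uses the descriptive label to explain the absence of a sample size calculation, whereas 3.2 sets out to pick a score. Using existing scores does not help, because the cut-offs are still estimated here. An interval alone would also leave the published point estimates too favourable in expectation. Nor can specificity and PPV be called unaffected without qualification: that depends on a mortality denominator the plan does not state.

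**Conclusion.** The point holds. As written, the rule in 11.1 gives in-hospital mortality sensitivity, LR+ and LR− that are too favourable in expectation, and nothing in the plan would show the reader how imprecise they are.

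The expected excess in sensitivity is about 1.5–4.5 points at 60–75 deaths, 3–10 at 18–30, and 0.5–2 at 180–225. Imprecision is the larger quantity in each case. Specificity and PPV are barely moved if all enrolled patients are analysed, but by up to about 0.6 and 2 points if only admitted patients are. The AUC is free of this bias but is planned without any measure of uncertainty.

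The direction did not depend on the assumptions tried. The size rests on the assumed AUC, score levels, admitted share and final enrolment, none of which the plan gives. The bias simulation treats patients as independent. Since a secondary objective is affected and the remedy needs no new data, the change should be made but is not critical.

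**What to change.** Add to Section 11.1:

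(a) *For in-hospital mortality, the whole Youden cut-off selection is repeated in a bootstrap that resamples sites. Optimism-corrected sensitivity, specificity, PPV, NPV, LR+ and LR− are reported beside the apparent values, with the bootstrap distribution of the selected cut-off.*

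(b) *All accuracy measures, including the AUC, are reported with 95% confidence intervals and the number of events for each score and endpoint. The mortality denominator (all enrolled or admitted patients) is stated.*

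(c) *Scores are compared by paired AUC differences with 95% confidence intervals from the same site bootstrap.*

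For mortality under (b), a workable choice is a Wilson interval at the corrected sensitivity, and site-bootstrap percentile intervals shifted by the estimated optimism for the other cut-off measures. This was checked by simulation with 45 sites of 25 and moderate between-site variation (assumed). At about 68 deaths, mean sensitivity bias fell from 1.3–4.2 points to between −0.2 and 1.2, and the Wilson interval covered 93.6–95.3%. At about 22 deaths, bias fell from 4.1–8.4 to 0.6–2.5 points, with coverage of 94.0–96.3%. The NPV interval under-covers (91–94% at about 68 deaths, 84–91% at about 22) and should be labelled approximate. Coverage of the paired AUC intervals was not tested.

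Cost: analysis wording and one short bootstrap program, with no new data and no change for patients or sites. The mortality figures will look slightly less favourable and the intervals visibly wide. Section 10.3.1 routes protocol changes through the steering committee and local ethics committees, and 10.3.2 accepts none during recruitment. An analysis-only change can instead be set down in a separate analysis plan before the outcome data are examined.
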